5.3 Withdrawal of Patients and Study Termination

In accordance with the Declaration of Helsinki, each patient is free to withdraw from the study at any time without penalty or loss of benefits or other adequate treatments to which he/she is otherwise entitled.

Investigators also have the right to withdraw patients from the study in the event of illness, AEs, or other reasons concerning the health or well-being of the patient, or in the case of lack of co-operation. After withdrawal of a patient, the investigator is responsible for ensuring adequate

treatment and follow-up, although every effort should be made to complete all assessments at an End of Treatment visit as listed in Section 7.0.

Should a patient decide to withdraw after administration of the investigational medicinal product, or should the investigators decide to withdraw the patient, all efforts will be made to complete and report the observations up to the time of withdrawal as thoroughly as possible. A complete final evaluation at the time of the patient's withdrawal should be made and an explanation given of why the patient is withdrawing or being withdrawn from the study.

The reason, time, and date for withdrawal must be noted in the eCRF. If the reason for withdrawal is a clinical AE, monitoring will continue until the outcome is evident. The specific event must be recorded in the eCRF.

Patients who are withdrawn before completion of the first cycle of APR-246, carboplatin and PLD as prescribed will be replaced.

The study treatment will be discontinued at any time if any of the following situations occur; in the case of study termination by the Sponsor patients will be allowed to continue to receive the standard of care:

1. Completed 6 cycles of treatment.
2. Progressive disease per RECIST v1.1 criteria.
3. \geq Grade 3 APR-246 related toxicity that leads to a delay in dosing and that persists for more than 4 weeks from the last planned study drug administration or recurs after the maximum dose reduction, despite optimal supportive therapy.
4. Patient refusal.
5. Lost to follow-up/noncompliance.
6. Significant illness that can affect the patient's ability to comply with study procedures.
7. At the discretion of the Investigator.
8. Pregnancy.
9. Study termination by Sponsor.

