- If hematological recovery is inadequate by Day 42 of any cycle, the Investigator should discuss appropriate patient management with the Sponsor before allowing the patient to continue with study drug treatment. If the patient is showing signs of response, the Investigator may retain the patient in the study, but should assess the potential for further prolonged periods of marrow suppression and the associated adverse events as part of this decision process.
- In the event that a patient requires a second dose reduction of systemic chemotherapy or the initial recovery of hematologic parameters took longer than 14 days even with growth factor support, the Investigator may also consider a single level reduction in the dose of APR-246 in conjunction with a further dose reduction of chemotherapy per Table 4.

Table 4. Dose Modification of Systemic Chemotherapy for Hematological Toxicities in Arm A

Chemotherapy Modification	Treatment Delay	APR-246 Dose Modification
Initial Dose Reduction	Less than 14 days	None
	14 days or more	Reduce one level
Second Dose Reduction	Any	Reduce one level

For patients in Arm B:

- If hematological recovery is inadequate by Day 42 of any cycle after cycle 2, the Investigator should discuss appropriate patient management with the Sponsor.

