6.5.3 Hypersensitivity / Adverse Drug Reactions to Chemotherapy Agents

All patients will be carefully monitored for clinical features of hypersensitivity reactions. Should a hypersensitivity reaction to carboplatin occur during infusion, this must be discontinued and an attempt at desensitization may be made subsequently if deemed appropriate by the Investigator in discussion with the patient. The timing of this will be at the discretion of the Investigator depending on the initial dose of carboplatin received.

Desensitization should be performed according to local practices and monitoring.

The desensitization procedure should take place with resuscitation facilities within easy access with regular observations and a trained nurse present throughout administration of APR-246 and chemotherapy. If at any point during the dose escalation allergic signs or symptoms are apparent, the carboplatin infusion must be discontinued.

All subsequent cycles should then be given using this procedure.

If it is not possible for the patient to continue to receive carboplatin due to unmanageable hypersensitivity, the Investigator in consultation with the Sponsor can consider either to remove the patient from the study or change to cisplatin monotherapy. Cisplatin monotherapy will be administered in place of the combination chemotherapy on day 4 of all remaining treatment cycles, up to a maximum of 6 cycles (including prior combination chemotherapy).

The cisplatin monotherapy should be administered, monitored and modified according to the local practices at the investigational site.

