6.6 Concomitant Treatment and Prohibited Medication

Patients are allowed to receive supportive care therapies (including cytokine, growth factors) concomitantly during the trial.

No anti-cancer therapy other than that given in this clinical trial; no immunotherapy; no hormonal cancer therapy; no radiation therapy (except palliative); and no experimental medications are permitted during the trial. All alternative therapies must first be approved by the Sponsor.

No poly (adenosine diphosphate [ADP]) ribose polymerase inhibitors are permitted until progression of disease (PD).

Concomitant use of paracetamol (acetaminophen) based compounds is allowed. However, caution should be taken when co-administrating APR-246 with high doses of paracetamol (i.e. 4 g/24 hrs). Use of paracetamol must be terminated if any liver function tests increase above normal ranges is detected.

Any disease progression that requires other specific antitumor therapy will be cause for discontinuation from the trial.

Antioxidants: Concomitant intake of acetylcysteine or other antioxidants might have a negative effect on the treatment efficacy and is therefore not recommended.

Anticoagulant therapy: Patients who are taking warfarin may participate in this trial; however, it is recommended that prothrombin time (INR and APTT) be monitored carefully at least once per week for the first month, then monthly if the INR is stable. Subcutaneous heparin is permitted.

Concurrent or procedural medications or therapy given to or taken by the patient will be recorded in the CRF along with the indication. All concomitant medications should be recorded for up to 30 days following the last protocol treatment. After this period, only relevant medication (e.g. medication in patients with treatment related AEs) will be recorded in the CRF.

Both generic and trade names may be recorded. However, the generic name is generally preferred because of its specificity, whereas trade names are preferred for combination products.

The potential interaction of APR-246 with other medicinal products has not been investigated.

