3. LVEF assessed by echocardiography between day 21 of cycle 2 and start of cycle 3, and day 21 of cycle 4 and start of cycle 5. LVEF is mandatory before each additional administration of PLD that exceeds a lifetime cumulative anthracycline dose of 450 mg/m². Additional echocardiograms can be conducted if clinically indicated per institutional practices.

4. ECG will be monitored as per the standard of care for PLD treatment.
5. One tumor biopsy to be performed within 4 weeks prior to day 1 APR-246 infusion and one tumor biopsy to be performed cycle 1, day 3, per laboratory manual (optional).
6. For sparse PK sampling schedule on Cycle 1, days 1, 2, and 4, please refer to Section 8.4.
7. Only Cycle 2 day 1, 4, 5 and Cycle 6, day 1.
8. Blood samples should be taken at each follow up visit until progression, as per laboratory manual.
9. To be performed the first 4 follow up visits only.
10. QoL to be performed at each radiological tumor assessment time point.
11. Physical examination only, excludes ECOG.
12. Patients to be followed until death. Survival after progression will be monitored (e.g. via telephone, via General Practitioner or via review of medical records) every 6 months. The start date of the first subsequent treatment will be collected and recorded.
13. 18-72h after the end of infusion of APR-246.
14. End of treatment (EoT) visit should take place 7 days after the completion of 6 cycles of chemotherapy (between day 28 and day 35 of cycle 6) or up to 30 ± 2 days after the last administration of APR-246 if treatment is stopped early for any reasons.
15. The first follow-up visit should commence 2 months (± 2 weeks) after the EoT visit. Subsequent follow-up visits should be performed every 3 months (± 2 weeks) until documented disease progression as defined by RECIST v1.1.

Table 10. Schedule of Study Evaluations in Arm B

	Pre-treatment ¹	Cycle 1				Cycle 2 and subsequent cycles					EoT ¹³	FU ¹⁴
		1	2	3	4	1	2	3	4	25-28		
Day			1	2	3	4	1	2	3	4	25-28	
Eligibility Criteria	X											
Registration/Randomization and Informed Consent	X											
Medical History	X	X*										
Quality of Life Questionnaires	X										X ⁹	X X ⁸
Tumor Assessment ²	X										X	X X
Physical Exam/ECOG	X	X*				X					X	X ¹⁰
Vital Signs	X	X				X						
Hematology/Coagulation	X	X*				X*					X	
Blood Chemistry	X	X*				X*					X	
Creatinine Clearance	X											
CA-125		X*				X*					X	X ⁷
Urinalysis	X	X*				X*						

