7.2.6 Follow-up Visits

The first follow-up visit should commence 2 months (\pm 2 weeks) after the end of treatment visit. Subsequent follow-up visits should be performed every 3 months (\pm 2 weeks) until documented disease progression, as defined by RECIST v1.1.

- **Physical examination:** Description of external signs of cancer until progression.
- **QoL questionnaires (first four follow up visits only)**
- **CA-125:** Disease will be followed by GCIG Criteria until progressive disease and then confirmed by CT scan/MRI.
- **Exploratory biomarkers:** Blood samples taken at each visit until progression. Refer to laboratory manual for detailed instructions.
- **Tumor Assessment (by CT/MRI):** Tumor assessments by a CT scan/MRI will be performed 2 months (\pm 2 weeks) after the end of treatment visit and every 3 months (\pm 2 weeks) thereafter, until the documented disease progression, as defined by RECIST v1.1.

All patients will be followed until initial progression. Information on survival and subsequent therapies will be collected.

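### Section 5.3 permits withdrawal from the study, not only from treatment, without saying that scans and survival contacts continue; this conflicts with Sections 7.1 and 7.2.6 and can cause avoidable, possibly arm-unequal PFS censoring

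*Combined protocol and SAP*

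**What the plan says.** **Text that lets a patient leave the study**

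- Section 5.3: "Investigators also have the right to withdraw patients from the study in the event of illness, AEs, or other reasons concerning the health". Poor co-operation is a further ground. On data it says that "all efforts will be made to complete and report the observations up to the time of withdrawal as thoroughly as possible". It adds a final evaluation, the End of Treatment assessments, monitoring of an adverse event that caused the withdrawal, and a general duty to ensure adequate care and follow-up.
- Section 6.5.3, on unmanageable carboplatin hypersensitivity: the investigator, with the sponsor, may consider "either to remove the patient from the study or change to cisplatin monotherapy".
- Section 6.6: "Any disease progression that requires other specific antitumor therapy will be cause for discontinuation from the trial".
- Section 6.5.2.1, Arm A, after inadequate hematological recovery by Day 42: "If the patient is showing signs of response, the Investigator may retain the patient in the study". The Arm B bullet has no such sentence.
- Section 6.5.2.2: if dosing is not possible within four weeks, the sponsor is consulted on whether the patient proceeds in the study.

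**Text that keeps every patient in follow-up**

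- Section 7.2.6: "All patients will be followed until initial progression", with survival and subsequent therapy collected.
- Section 7.1, Table 9 footnote 12 and Table 10 footnote 11: "Patients to be followed until death". Section 7.2.7 sets survival contacts every six months after progression, remotely if need be.

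**Analysis.** PFS is censored at the last evaluable tumor assessment (Section 9.1) and OS at the last known alive date (Section 9.5.2.2). The primary population is all randomized patients (Section 9.4). Treatment is not blinded (Section 9.6).

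**The concern.** Section 5.3 contains a separate numbered list of situations that stop study treatment, so the protocol knows the difference between leaving treatment and leaving the study. It does not carry that difference into the withdrawal paragraphs. A patient withdrawn there owes the trial an end-of-treatment assessment and nothing later that bears on PFS.

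Stopping for toxicity or illness may well be related to prognosis. The investigator knows the arm when deciding, only Arm A carries the added drug's toxicity, and the retention sentence that mentions response is in Arm A alone. If patients with a worse outlook are censored more often in Arm A than in Arm B, the PFS hazard ratio moves in favor of APR-246. Section 9.5 describes no sensitivity analysis for such censoring. Section 9.3 intends moderate or large effects to support conditional approval, and the 0.023 level was chosen to keep overall error below 0.025, so there is little slack.

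**Working it through.** **1. The texts side by side.** Take a patient withdrawn by the investigator for an adverse event, without progression.

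| Question | Section 5.3 | Sections 7.1, 7.2.6, 7.2.7 |
|---|---|---|
| End of Treatment assessments? | Yes | Yes |
| Later scans to progression? | Not stated; data requested up to withdrawal | Yes, all patients |
| Survival contacts? | Not stated | Yes, until death |

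No sentence says which text governs. If the site follows 5.3, Section 9.1 censors PFS at the last evaluable scan.

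**2. Who is covered by the duty to complete observations.** The sentence in 5.3 has two branches. The first begins "Should a patient decide to withdraw after administration of the investigational medicinal product", so it omits patient-initiated withdrawals in Arm B and in patients not yet dosed. The second, withdrawal decided by the investigator, carries no dosing condition and covers both arms.

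**3. Size under assumptions.** The documents give no withdrawal rate, so this is an illustration.

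Inputs from the plan: 400 patients at 1:1 (Section 9.8.2); final analysis 12 months after the last enrollment and one-sided level 0.023 (Section 9.5.2.1).

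Assumptions: exponential PFS with control median 11.3 months (the carboplatin/PLD figure cited in Section 2.2); accrual 12 per month; true hazard ratio 1; in both arms a share q stops treatment at a uniform time in months 0 to 6 and then has k times the hazard. The test is an unstratified logrank at fixed N, without interim looks, and censoring falls on the withdrawal date rather than the last scan. There are 6,000 runs per setting.

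Check on the plan's own level: with everyone followed, rejection is 0.020 to 0.029 over 48 settings, against 0.023. The Monte Carlo standard error is √(0.023 × 0.977 / 6000) = 0.0019, so differences below about 0.006 should not be read.

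Fully unequal case, k = 2: all such Arm A patients censored, all such Arm B patients followed. The last column is a hand check, 1 − Φ(1.995 − |ln HR| × √(events/4)), using the events after censoring.

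| q | Events: followed, then censored | HR when censored | Simulated error | Hand check |
|---|---|---|---|---|
| 5% | 320, 313 | 0.974 | 0.042 | 0.039 |
| 10% | 323, 308 | 0.951 | 0.058 | 0.060 |
| 15% | 326, 303 | 0.930 | 0.082 | 0.086 |
| 20% | 329, 298 | 0.906 | 0.121 | 0.126 |

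For q = 10%: |ln 0.951| = 0.0502; √(308/4) = 8.775; product 0.441; 1.995 − 0.441 = 1.554; upper tail 0.060.

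How far this depends on the assumptions:

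- Half of the similar Arm B patients also censored, k = 2: 0.029, 0.041, 0.046 and 0.062 for the same four shares.
- k from 1.5 to 3, fully unequal: 0.037 to 0.046 at 5%, and 0.039 to 0.080 at 10%.
- Equal censoring in both arms, or unchanged later hazard (k = 1): about 0.020 to 0.026, that is, no movement.

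The stated power of about 0.70 (Section 9.8.4) plays no part here.

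**The case against.** The strongest reply is that the protocol already separates the two ideas. The numbered list in 5.3 stops treatment only, including for APR-246-related toxicity, significant illness and investigator discretion. Section 7.2.5 schedules an End of Treatment visit after early stopping for any reason, with a CT or MRI, and 7.2.6 runs follow-up scans from that visit to progression. Section 5.3 sends withdrawn patients to the same visit. On this reading most toxicity stops stay in follow-up. That stands, and it narrows the gap to patients withdrawn from the study as such. It does not close it, because no text returns those patients to the 7.2.6 schedule.

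Several stronger readings are tempting but unsupported:

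- *Patients must be removed.* A reader might infer this, but 5.3 gives a right, 6.5.3 offers one of two options and 6.5.2.2 calls for a discussion. Only 6.6 is worded firmly, and it applies after progression.
- *Non-responders are removed.* No section gives lack of response as a ground. It could be inferred only from the Arm A sentence in 6.5.2.1, whose preceding sentence concerns continuing study drug. Retaining responders does not mean that others leave follow-up.
- *The duty to complete observations never reaches Arm B.* The investigator branch does reach it (step 2).
- *OS is cut short at progression.* Section 6.6 alone might suggest so, but the table footnotes and 7.2.7 plan survival contacts after progression and collect the start of the next treatment.
- *The all-randomized analysis is contradicted.* Section 9.4 defines who is analyzed; withdrawn patients stay in and are censored.
- *The hazard ratio will be biased.* That needs withdrawal that is both prognostic and unequal between arms. Carboplatin and PLD toxicity occurs in both arms, and the documents give no rates.

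**Conclusion.** The conflict is real and worth removing. Section 5.3, supported by 6.5.3 and 6.6 and by loose wording in 6.5.2.1 and 6.5.2.2, allows study-level exit that Sections 7.1 and 7.2.6 do not provide for. The consequence is a possible bias in PFS, not a demonstrated one.

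Under a true hazard ratio of 1, one-sided error is about 0.04 to 0.06 instead of 0.023 if 5 to 10% of Arm A stop early, have doubled later hazard and are censored while similar Arm B patients are followed. It is about 0.03 to 0.04 if half of those Arm B patients are censored too, and unchanged if withdrawal is equal or non-prognostic. These figures rest on the assumed accrual, control median, stopping times and later hazard, and on a fixed-size unstratified test. They show an order of magnitude, not a forecast. The OS risk is smaller, because remote survival follow-up is planned, but 6.6 should be brought into line with it.

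The case for acting is mainly that the repair is cheap and that scans not taken after withdrawal cannot be recovered later.

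**What to change.** In Section 5.3, state that:

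- stopping study treatment, for any reason and in either arm, including patients never dosed, does not end study participation;
- the Section 7.2.6 scans to RECIST progression and the Section 7.2.7 survival contacts continue unless the patient withdraws consent to follow-up or is lost to follow-up;
- the branch on patient-initiated withdrawal applies from randomization, not from administration of the investigational product.

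Record treatment discontinuation and withdrawal from follow-up as separate eCRF items, each with date and reason.

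Reconcile Sections 5.3, 6.5.2.1, 6.5.2.2, 6.5.3 and 6.6 with the Table 9 and Table 10 footnotes and Section 7.2.6 on follow-up only. The rules on who continues, changes or stops treatment are clinical and should be left untouched. In particular, replacing study with study treatment in 6.5.2.1 would tie continued treatment to response, which is not the purpose here.

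Cost: protocol wording and a small eCRF change. The scans and contacts are already planned. The downside is that sites must keep contact with patients who have stopped treatment.

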4.2 Randomization/Registration of Patients

Upon completion of all screening evaluations, the center will register the patient using the Interactive Web Response System (IWRS). After successful completion of patient registration, a treatment assignment and randomization number will be issued.

Once the patient is registered through the IWRS, the patient is considered enrolled in the study. Specific instructions for the central enrolment and registration procedures are provided to the center in the Study Operations Manual.

Registered patients will be assigned a unique patient identifier number. If a patient is withdrawn and replaced (as described in Section 13), the patient identifier number will not be reused.

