4.4 Treatment Allocation

Patients will be randomized in a 1:1 ratio to receive the carboplatin/PLD chemotherapy regimen with or without APR-246. The study treatment will not be blinded. Patients will be registered on-study as described in Section 4.2; the treatment arm will be automatically allocated during registration.

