9.4 Analysis Populations

All randomized subjects will be analyzed according to the group in which they were randomized.

Intent-to-Treat (ITT): All randomized patients will be included in the intent-to-treat (ITT) population. The ITT population will serve as the primary analysis population for efficacy.

Safety Evaluable Population: All randomized patients who received any amount of study medication (APR-246, carboplatin, or PLD) will be considered evaluable for safety, regardless of the duration of treatment. This population will be used to summarize all safety parameters.

Efficacy Evaluable Population: All randomized patients with pre-treatment measurable disease by RECIST v1.1 who have at least one radiographic assessment after pre-treatment or discontinue study medication early due to disease progression and have a TP53 mutation will be considered evaluable for efficacy. The efficacy-evaluable population will be the secondary analysis population for efficacy.

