9.8.1 Timing of Interim Analyses

Interim analyses will occur when 150, 200, 250, 300, and 350 patients are enrolled.

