9.8.2 Allocation

The trial will enroll up to a maximum of 400 patients, with randomization to treatment and control in a fixed 1:1 ratio. Stratified randomization will be used. The stratification factors are prior lines of platinum-based treatment (1,2), platinum free interval (6-12, 12-24 months) and BRCA status (known positive versus other).

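### Does replacing patients withdrawn during cycle 1 undermine the all-randomised primary analysis or the 400-patient cap?

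*Combined protocol and SAP*

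**What the plan says.** The replacement rule is one sentence in Section 5.3: "Patients who are withdrawn before completion of the first cycle of APR-246, carboplatin and PLD as prescribed will be replaced". It is not restricted to Phase Ib and names no arm. Section 4.2 mentions replacement once more: "If a patient is withdrawn and replaced (as described in Section 13), the patient identifier number will not be reused". Section 13 is the list of references.

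Four other statements decide what the rule can do in Phase II:

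- Enrolment (Section 4.2): "Once the patient is registered through the IWRS, the patient is considered enrolled in the study".
- Allocation (Section 4.4): "the treatment arm will be automatically allocated during registration".
- Analysis (Section 9.4): "All randomized patients will be included in the intent-to-treat (ITT) population", with ITT as the primary efficacy population, and "All randomized subjects will be analyzed according to the group in which they were randomized".
- Counts (Sections 9.8.2 and 9.8.1): "The trial will enroll up to a maximum of 400 patients" and "Interim analyses will occur when 150, 200, 250, 300, and 350 patients are enrolled".

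No section says that a replaced patient leaves the ITT population or the enrolled count, or that a replacement inherits an allocation.

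**The concern.** Replacement belongs naturally to dose finding, where a cohort needs patients who have completed the assessment period. In a randomised comparison it raises three worries.

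First, the trigger occurs after randomisation and depends on getting through treatment. Arm A has four days of APR-246 infusions with chemotherapy on Day 4; Arm B has chemotherapy on Day 1 and no APR-246. If replaced patients dropped out of the primary analysis, Arm A could be left with its better-tolerating patients, and a one-sided test at 0.023 would be anti-conservative.

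Second, if replaced patients stay in and replacements are added on top, enrolment could pass 400 and the interim triggers would be unclear.

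Third, if a replacement took over the withdrawn patient's assignment in this open-label trial, that assignment would be known in advance.

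**Working it through.** **1. The plan's own figure.** Section 9.8.4 gives about 0.70 power at a hazard ratio (HR) of 0.70. For a fixed design with a one-sided 0.023 test, the Schoenfeld formula gives

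events = 4(1.995 + 0.524)² / (ln 0.70)² = 4 × 6.35 / 0.1272 ≈ 200.

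An approximate simulation of the adaptive rules gave power of 0.58 to 0.72, counting any final rejection. It assumed control medians of 9.4 to 11.3 months (the two PFS medians quoted in Section 2.2) and accrual of 8 to 24 patients per month. The stated figure is attainable at slow accrual but cannot be confirmed, because Appendix V is redacted. The formula contains no replacement term.

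**2. What happens to a patient withdrawn in cycle 1.**

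| Question | Text that answers it | Answer |
|---|---|---|
| Already randomised? | 4.4: arm allocated during registration | Yes |
| In the primary analysis? | 9.4: all randomised, as randomised | Yes |
| Counted toward 150 to 350 and 400? | 4.2: enrolled at registration; 9.8.1 and 9.8.2 count enrolled patients | Yes |
| Is the assignment passed on? | 4.2: identifier not reused; 4.4: automatic allocation; 9.6: central permuted-block randomisation | Nothing says so |

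A replacement is therefore most naturally a further registration with its own randomisation, which counts like any other.

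**3. Effect on the test.** Fixed-size simulation: 2,500 trials per cell, accrual 12 per month, control median 11.3 months, one-sided 0.023 logrank. Assumed early withdrawal (Arm A/Arm B) was 5%/2%, 10%/2% or 15%/5%. Withdrawal was either unrelated to prognosis or drawn from a 20% group with two or three times the hazard. The documents give no such rates.

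| Handling | Type I error | Power at HR 0.70 |
|---|---|---|
| Kept in ITT, 400 in total | 0.020 to 0.027 | 0.73 to 0.83 |
| Kept in ITT, replacements added | 0.018 to 0.025 | 0.77 to 0.85 |
| Dropped, unrelated to prognosis | 0.022 | not comparable |
| Dropped, poor-prognosis group | 0.036 to 0.108 | not comparable |

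The Monte Carlo standard error at 0.023 is √(0.023 × 0.977 / 2500) = 0.003, so the first two rows are nominal. In the last row the average HR under the null moves to between 0.985 and 0.92. That row contradicts Section 9.4.

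**4. Overrun, if 400 meant patients net of withdrawals.** Number randomised = 400/(1 − w), where w is the average withdrawal rate over the two arms, rounded up:

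- 2%/2%: 400/0.98 = 409
- 5%/2%: 400/0.965 = 415
- 10%/2%: 400/0.94 = 426
- 10%/5%: 400/0.925 = 433
- 15%/5%: 400/0.90 = 445

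The text counts enrolled patients, so this net reading is not the stated one.

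**5. A rough size for the bias.** Suppose 8% of Arm A and 2% of Arm B withdraw and have twice the hazard. The ratio of average hazards at time zero is (0.92 + 0.08 × 2)/(0.98 + 0.02 × 2) = 1.08/1.02 = 1.059. That is not the trial's HR, because the high-hazard patients leave the risk set early. Simulating these inputs with exponential PFS (200,000 patients per setting, standard error about 0.006) gives a Cox HR of 1.03 to 1.06, depending on the control median and on whether follow-up is 12 months or 12 to 36 months. About 1.06 is thus the top of the range. The difference would be hidden only if those patients were excluded.

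**The case for a change.** The best argument for acting is that the sentence is live. The dose-confirmation part is complete, so the rule now governs only the randomised part, and Section 4.2 repeats it. The plan does not say in so many words that replacement stays within 400, nor how the rule works for Arm B. A design meant to support conditional approval, with its level set by simulation, should not leave the enrolled set to inference, and the wording would cost two sentences to mend.

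Much of this stands as a comment on drafting. The sentence does not fit Arm B, the cross-reference is dead, and an explicit statement about the cap is absent. The wording suggests a leftover from Phase Ib, though that is an inference.

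The claimed consequences do not stand. Exclusion from the primary analysis runs against Section 9.4. An overrun needs a net count that Section 4.2 does not support. A predictable assignment needs slot reuse that no section describes. With withdrawn patients kept, adding a newly randomised patient does not select tolerant patients into Arm A. Any dilution comes from retaining early withdrawals under ITT, which would happen with or without replacement.

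One related exposure is real but separate. A patient who withdraws in cycle 1 with no later scan contributes little under the PFS censoring rule. Sections 5.3 and 7.2.6 ask for an End of Treatment assessment and follow-up to progression, and deleting the replacement sentence would not affect this.

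**Conclusion.** The concern does not hold as a threat to the primary result. Followed as written, the plan analyses every randomised patient in the allocated arm and counts each from registration. Type I error with withdrawals kept and replaced was 0.018 to 0.025 against 0.023. Removing the rule would leave the maximum of 400, the interim triggers and the 0.023 level as they are.

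The residue is a clerical slip and a small gap that a trial team would fill from Sections 4.2 and 9.4. Tidying the wording would be harmless but would not alter a design figure or an analysis.

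This rests on the ITT definition being applied literally and on replacements being randomised in the ordinary way. The simulation used a fixed sample size, not the full adaptive rules, and its withdrawal rates, accrual and prognosis link are assumptions. If the sponsor intended to exclude replaced patients from the primary analysis, the conclusion would reverse, but nothing in the documents says so.
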